Appendix Appendix	

#### ABBREVIATIONS AND DEFINITIONS OF TERMS

AE Adverse event

ALT Alanine aminotransferase AST Aspartate transaminase

AUC Area under curve for pharmacokinetic concentration vs time profile

AUCinf Area under curve from time 0 extrapolated to infinity

AUClast Area under curve from time 0 to the last measured concentration

BID Twice daily
BMI Body mass index
CI Confidence interval

Cmax Maximum observed concentration

CrCl Creatinine clearance CRF Case report form

CRO Contract research organization

CRU Clinical research unit CSR Clinical study report

DENV Dengue virus ECG Electrocardiogram

eGFR Estimated glomerular filtration rate

ET Early Termination

FDA Food and Drug Administration
FSH Follicle-stimulating hormone
GCP Good Clinical Practice
GLP Good Laboratory Practice
hCG Human chorionic gonadotropin

HED Human equivalent dose

HREC Human research ethics committee

ICF Informed consent form

ICH International Council for Harmonisation
IND Investigational New Drug application
INR International Normalized Ratio

IUD Intrauterine device

J&J Johnson & Johnson Pharmaceutical Research & Development, LLC

LSM Least-squares means

MPR N-(4-methoxyphenyl) retinamide

NCI National Cancer Institute NDA New Drug Application

NOAEL No-observed-adverse-effect level

OTC Over-the-counter
PD Pharmacodynamics
PK Pharmacokinetics

QTC QT interval corrected for heart rate

SAD Single ascending dose
SAE Serious adverse event
SAP Statistical Analysis Plan
SRC Safety Review Committee

SUSAR Suspected unexpected serious adverse reaction

T1/2 Terminal elimination half-life

TB Tuberculosis

Tmax Time to achieve maximum concentration

TEAE

Treatment-emergent adverse event Urine drug screen Upper limit of normal United States UDS ULN

US

#### 1 INTRODUCTION

#### 1.1 Background

An estimated 3.9 billion people in more than 125 countries are at risk of dengue fever, with approximately 390 million infections occurring annually. These infections lead about 500,000 persons to require hospitalization due to dengue each year, and about 20,000 deaths occur due to severe dengue every year (WHO, 2018). Dengue is a mosquito-borne infection caused by the dengue virus (DENV) and is found in tropical and sub-tropical climates worldwide, mostly in urban and semi-urban areas. The severe form of the disease is a leading cause of serious illness and death in some Asian and Latin American countries (WHO, 2021). Endemic areas include some United States (US) territories and freely associated states. In 2021, 63 dengue cases were reported in the US and 435 cases were reported in US territories (CDC, 2021; CDC, 2022). Importantly, there is no specific treatment for dengue infection.

Dengue prevention and control is based on vector control measures, which require sustained community involvement and usually are not highly effective in preventing disease transmission. The first dengue vaccine, Dengvaxia® (CYD-TDV), developed by Sanofi Pasteur, was licensed in 2015 and has now been approved in about 20 countries, including the US (Food and Drug Administration [FDA]-approved in 2019) (FDA, 2020; WHO, 2021). The vaccine was considered a major breakthrough in the prevention of DENV infection; however, results of a retrospective analysis showed that trial subjects who were seronegative at time of first vaccination had a higher risk of more severe dengue and hospitalizations from dengue compared with unvaccinated subjects. In addition, the vaccine is not licensed for people younger than 9 years and older than 16 years of age. Thus, the use of Dengvaxia is restricted to children (9 to 16 years) living in endemic areas who have previously had at least 1 documented DENV infection (WHO, 2018; WHO, 2021; CDC, 2022).

Recently, a new dengue vaccine, QDENGA®, was approved for use regardless of prior exposure and without the need for pre-vaccination testing. Approval was based on results across 19 Phase 1, 2, and 3 trials with more than 28,000 children and adults, including 4.5 years of follow-up data showing sustained efficacy and no important safety risks. This vaccine is approved for use in Brazil, Indonesia, and in Europe, and was granted priority review for its Biologics License Application by the FDA (Takeda, 2023).

In view of the current situation, there is an unmet medical need for therapies focusing on the prophylaxis of dengue infection, aiming to minimize viral transmission in endemic areas. To answer to this need, Island Pharmaceuticals Ltd (also referred to as the Sponsor) is developing the ISLA101 product, an immediate-release oral capsule of fenretinide (100 mg), for the prophylaxis of dengue fever.

#### 1.2 Fenretinide

Fenretinide (4-[hydroxyphenyl]retinamide; also known as 4-HPR) is an analog of all-trans-retinoic acid, first synthesized in the 1960s as an alternative to naturally occurring retinoids to treat skin diseases. Since then, nonclinical and clinical studies have demonstrated that this drug has lower toxicity when compared to other retinoids and exhibits cytotoxic

activity in a variety of cancer types (Cooper et al., 2017). According to the FDA's Approved Drug Products with Therapeutic Equivalence Evaluations (also known as the "Orange Book"), there are currently no marketed or discontinued drug products in the US that include fenretinide as the active ingredient.

Fenretinide has been used to treat cancer patients for decades with a favorable safety profile. To strategically support the development of ISLA101 for the prophylaxis of dengue fever, the Sponsor obtained the right of reference to Investigational New Drug application (IND) 38892, which focused on fenretinide for the treatment of cancer, psoriasis, and acne. IND 38892 was initially sponsored by Johnson & Johnson Pharmaceutical Research & Development, LLC (J&J), and later by the National Cancer Institute (NCI) and was withdrawn in 2003 due to non-satisfactory efficacy data. The Sponsor developed a formulation very similar to the previous formulation, to facilitate bridging and reliance on safety information from IND 38892.

While tumor responses have been minimal, the established safety profile makes fenretinide a desirable candidate for drug repurposing. In a high-throughput screen to identify compounds that inhibit the binding of the DENV NS5 to host nuclear import proteins, IMP- $\alpha$  and IMP- $\beta$ 1, fenretinide was identified. Using a lethal mouse model of DENV, it was demonstrated that fenretinide is effective in protecting against DENV1-4 infections, possibly by targeting NS5 (Fraser et al., 2014). In a second study that targeted the identification of anti-DENV compounds, the screening of a library of bioactive lipids and modulators of lipid metabolism also identified fenretinide as an inhibitor of DENV replication in vitro and within an in vivo mouse model, through an unknown mechanism (Carocci et al., 2015). These studies unveiled the potential of fenretinide as an anti-dengue therapy.

#### 1.2.1 Clinical Experience

To date, there are no studies in humans that evaluate the efficacy of fenretinide to prevent DENV infection. However, the safety profile of fenretinide has been thoroughly described in 5 clinical pharmacology studies conducted under IND 38892, to which Island has right of reference, and in clinical studies from the published literature.

Clinical studies conducted under IND 38892 and the published literature characterize fenretinide as well-tolerated and did not identify major safety concerns. A total of 3487 healthy subjects (3273 from the literature and 214 from IND 38892, including approximately 150 pediatric subjects) have been exposed to fenretinide. Of the subjects exposed, 3188 healthy subjects (2974 from the literature and 214 from IND 38892) were treated with the oral capsule formulation provided by the NCI or J&J, which was the subject of IND 38892. Despite the high number of exposed subjects, at doses up to 4000 mg/m²/day, the most common adverse events (AEs) reported for all subjects treated with oral fenretinide were mild and included headache, diarrhea, nausea, skin irritation, and nyctalopia. No deaths or serious adverse events (SAEs) were reported in studies with fenretinide administered orally.

# 1.2.1.1 Teratogenicity

Oral retinoids, such as isotretinoin (13-cis retinoic acid), are known to produce teratogenic effects in animals and in humans, therefore representing a clinical concern when used to treat female patients of childbearing potential. Isotretinoin is approved in the US for the treatment of severe recalcitrant nodular acne in non-pregnant patients 12 years of age and older, although due to its teratogenicity, isotretinoin is marketed only under a special restricted distribution program (FDA, 2021).

Fenretinide is a retinoid, and teratogenicity risks are a concern, even though the teratogenic effects of fenretinide have been shown to be milder at higher doses when compared with other retinoids such as isotretinoin. In reproductive and developmental toxicity studies conducted under IND 38892, the most biologically significant events in the offspring of rats involved ocular toxicity and delayed ossification of skull bones (doses up to 800 mg/kg, HED = 4774.2 mg/m²). In rabbits, a low incidence of tail, cleft/palate, and limb malformations were observed in the offspring from mid- and high-dosage groups (doses up to 800 mg/kg, HED = 9548.4 mg/m²).

Clinical studies in healthy volunteers from IND 38892 were conducted in males, to avoid the risk of teratogenic effects. In studies in patients with ichthyosis, psoriasis, multiple basal cell carcinoma, and treatment-resistant acne, 16 females and 79 males were exposed to 600 and 800 mg daily doses of fenretinide (370 and 493.3 mg/m² for 60 kg humans) for up to 16 weeks (mean length of therapy was 66.57 days for all patients). No pregnancy cases were reported. Fenretinide has also been tested in clinical research for decades without significant teratogenic events being reported. In over 30 clinical studies in the published literature, approximately 2560 female subjects were exposed to fenretinide at doses ranging from 61.7 to 4000 mg/m²/day for up to 5 years; no teratogenicity issues were reported in these studies.

#### 1.3 ISLA101

ISLA101 is an oral capsule formulation of fenretinide. Island plans to submit a New Drug Application (NDA) for ISLA101 for the prophylaxis of dengue fever via the 505(b)(2) regulatory pathway. To support the ISLA101 NDA, Island intends to rely on clinical and nonclinical studies from IND 38892 and from the published literature, in addition to Sponsor-conducted studies.

The current Phase 1 study will evaluate the safety, tolerability, and pharmacokinetics (PK) of single ascending doses of fenretinide after administration of ISLA101 (at doses of 300, 600, and 900 mg/m²) in healthy subjects. This study will also assess the dose proportionality of systemic exposure of ISLA101 and food effect as an exploratory objective. To safeguard against the possible risk of teratogenicity, the study will evaluate male subjects and female subjects who are not of childbearing potential. Contraception requirements compliant with local regulations and clinical practices are included as part of the inclusion criteria for the study.

#### 1.4 Risk and Benefits

The well-tolerated safety profile of fenretinide in clinical studies conducted under IND 38892 and in published literature, as evidenced by the absence of SAEs and low incidence of mild AEs, supports the safety of ISLA101. The healthy subjects who enroll in this study are not expected to derive direct benefit from study participation. The safety, tolerability, and PK data obtained in this study, however, are expected to support the development of a prophylactic for the treatment of dengue fever, thereby addressing an unmet medical need.

Previous nonclinical and clinical data indicate that retinoids have teratogenic potential, although the teratogenic effects of fenretinide have been shown to be milder compared to other retinoids. To promote subject safety, this study will only evaluate male subjects and female subjects of nonchildbearing potential. Female subjects will be excluded if they are pregnant or lactating, taking hormonal contraceptives (due to potential drug-drug interactions with fenretinide), or are less than 12 months postmenopausal or have had less than 6 weeks elapse following bilateral oophorectomy. As a safety measure, pregnancy testing will be conducted frequently during the study. Male subjects with female partners must agree to use appropriate contraceptive measures during the study, in keeping with the special restricted distribution program for isotretinoin (FDA, 2021), and in compliance with local regulations and clinical practice. If subject or partner pregnancy occurs, study drug will be discontinued, and the pregnancy will be promptly reported to the Sponsor for appropriate follow-up. Collectively, these safeguards and monitoring processes will promote subject safety, and the potential benefit of developing a therapy for the prophylaxis of dengue fever is thought to outweigh a potential teratogenic risk.

Overall, there is no potential benefit to healthy subjects, while the risks appear to be minimal based on the available safety data, study inclusion criteria, and study monitoring procedures.

#### 2 STUDY OBJECTIVES

# 2.1 Primary Objective and Endpoints

# 2.1.1 Primary Objective

The primary objective is to:

• Evaluate the safety and tolerability of single ascending doses of ISLA101 in healthy adult volunteers (fasted).

#### 2.1.2 Primary Endpoints

The primary endpoints are:

• Vital signs, clinical laboratory tests, changes from baseline in physical examinations, AEs, and treatment-emergent adverse events (TEAEs).

# 2.2 Secondary Objective and Endpoints

#### 2.2.1 Secondary Objective

The secondary objective is to:

• Characterize the PK profile (fasted) of fenretinide after administration of single ascending doses of ISLA101 in healthy adult volunteers.

#### 2.2.2 Secondary Endpoints

The secondary endpoints are:

• Single dose PK parameters for fenretinide in plasma: Cmax, Tmax, AUClast, AUCinf, T1/2, and others as relevant.

# 2.3 Exploratory Objective and Endpoints

# 2.3.1 Exploratory Objective

The exploratory study objective is to:

• Assess the PK profile of fenretinide in healthy adult volunteers under fed conditions.

# 2.3.2 Exploratory Endpoints

The exploratory endpoints are:

• Single dose PK parameters for fenretinide in plasma under fed conditions:  $C_{max}$ ,  $T_{max}$ ,  $AUC_{last}$ ,  $AUC_{inf}$ ,  $T_{1/2}$ , and others as relevant.

#### 3 INVESTIGATIONAL PLAN

#### 3.1 Overall Study Design

The study is a randomized, double-blind, placebo-controlled single ascending dose (SAD) study of ISLA101 (fenretinide oral capsules) to evaluate safety, tolerability, and pharmacokinetics in healthy human subjects. The study will consist of up to 4 cohorts that will evaluate dose levels of 300 mg/m² (fasted), 600 mg/m² (fasted), and 900 mg/m² (fasted). The highest tolerated dose level cohort will then be evaluated in a fed condition (in a crossover manner). Eight subjects will be enrolled per dose cohort, with 6 subjects receiving active drug and 2 subjects receiving placebo treatment in a blinded manner. Each subject will be allocated to 1 dose level only.

After completing screening activities, eligible subjects will enter the clinical research unit (CRU) on Day -1 for 5 days. Subjects will receive a single dose of study drug in the morning of Day 1 after an overnight fast of approximately 10 hours, followed by additional 4 hours fast after dose for PK sampling. Cohorts 1 through 3 will receive 300 mg/m², 600 mg/m², and 900 mg/m², respectively, under fasted conditions. After the safety review by the independent safety review committee (SRC), the dose level can be escalated to the planned or lower than planned dose level or de-escalated to an intermediate dose level. Decisions to proceed to the next cohort will be made by the Investigator, SRC, and Sponsor based on the safety data from previous cohort(s).

Safety data will be reviewed to identify the cohort that received the highest dose level under fasted condition. The subjects in this cohort will be recalled to evaluate the PK of ISLA101 under fed conditions (8 subjects; Cohort 4). In Cohort 4, subjects will fast for approximately 10 hours overnight and will consume a high-fat, high-calorie meal approximately 30 minutes prior to administration of study drug. No food consumption will be permitted for at least 4 hours post-dose.

For all cohorts, study drug will be taken with up to 240 mL of water. In fasted cohorts, water will be allowed ad libitum except the interval from 1 hour before to 1 hour after the dose. In the fed cohort, water will be allowed ad libitum except the interval from 1 hour before to 1 hour after dose.

Subjects will be discharged from the clinic on Day 5. At the discretion of the Investigator or designee, the confinement time can be extended to ensure the safety of each subject. Subjects will have up to 3 days of follow up. For Cohort 4 (the food effect cohort), the confinement and follow-up visit will be repeated. Subjects who are dosed but withdrawn prior to study completion will participate in an Early Termination visit and may be replaced if needed to obtain sufficient information as possible based on the timing.

In all cohorts, safety will be assessed via vital signs, clinical laboratory tests, physical examinations, AEs, and TEAEs. Pharmacokinetic data will be collected and analyzed at the end of the study but will not be used for dose escalation decisions. A description of study assessments is provided in Table 1.

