Study Design and Treatment	This study is a randomized, double-blind, placebo-controlled SAD study. There are 3 planned dose-level cohorts (Cohorts 1-3). Each dose-level cohort will consist of 8 subjects (6 active + 2 placebo), who will be treated under fasted conditions. The subjects in the highest tolerated dose-level cohort will also be administered ISLA101 under fed conditions, in a cross-over manner (Cohort 4). Proposed doses are 300, 600, and 900 mg/m² (equivalent to 8.1, 16.2, and 24.3 mg/kg). Each subject will be allocated to 1 dose level only.  The study will include a 5-day stay in the clinical research unit followed by a final safety follow-up visit at Day 8.  An independent Safety Review Committee (SRC) will review available safety data up to 96-hours post-dose for subjects enrolled in each dose-level cohort. After safety review, the dose level may be escalated to the next planned or lower than

planned dose level, de-escalated to an intermediate dose level, or repeated at the same dose, if needed.

The first 3 dose-level cohorts will be treated under fasting conditions. A single dose of study drug will be administered on the morning of Day 1, after an overnight fast of approximately 10 hours, followed by an additional 4-hour fast after dosing. Study drug will be taken with up to 8 oz/240 ml of water. Water will be allowed ad libitum except the interval from 1 hour before to 1 hour after dosing.

Following review of the safety data of the highest tolerated dose level, the subjects enrolled in this dose-level cohort will be recalled to evaluate the PK of ISLA101 dosed under fed conditions (Cohort 4; 8 subjects). These data will support a planned Phase 2 study. Subjects will be informed and will be provided a consent form prior to the participation in the food effect cohort (Cohort 4) of the study.

Subjects in Cohort 4 will be dosed after a meal. They will fast overnight for at least 10 hours and will then consume a high-fat, high-calorie meal prior to administration of study drug, as outlined in the FDA's Guidance for Industry- Assessing the Effects of Food and Drugs in INDs and NDAs – Clinical Pharmacology Considerations. The study drug should be administered approximately 30 minutes after start of the high-fat meal. No food consumption will be permitted for at least 4 hours post-dose. Water will be allowed ad libitum except the interval from 1 hour before to 1 hour after dose.

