#### 3.2 Rationale for Study Design

A randomized, double-blind study in healthy subjects is considered appropriate to evaluate the safety, tolerability, and PK of ISLA101. Single ascending doses of ISLA or placebo will be administered under fasting conditions, and safety and tolerability data will be evaluated in each cohort to guide doses administered to future cohorts. The highest tolerated dose will also be administered under fed conditions to assess any potential food effect (in a crossover manner). A rationale for dose selection is provided in Section 3.2.1.

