## 10.6 PK Analysis

Descriptive statistics for PK concentrations and parameters will consist of number of subjects (n), arithmetic mean, standard deviation (SD), geometric mean, geometric coefficient of variation (%), median, minimum, and maximum. For  $T_{max}$  and  $T_{1/2}$ , only n, median, minimum, and maximum will be presented.

This study will perform PK analysis using validated software, such as Phoenix® WinNonlin® version 8.0 or higher. Pharmacokinetic parameters will be calculated through noncompartmental analysis of fenretinide and its metabolites MPR and oxo-HPR, including  $C_{max}$ ,  $AUC_{last}$ ,  $AUC_{inf}$ ,  $T_{max}$ ,  $T_{\frac{1}{2}}$ , Cl/F, and V/F on the day of dosing. Other relevant parameters will also be estimated.

Dose proportionality for fenretinide exposure parameters ( $C_{max}$ ,  $AUC_{last}$ , and  $AUC_{inf}$ ) will be assessed statistically based on the natural log (ln)-transformed PK parameters. Proportionality analysis will be done using a Power Model defined as:

$$\ln (PK \text{ parameter}) = \alpha + \beta \cdot \ln (Dose) + \varepsilon$$

where  $\alpha$  is the intercept,  $\beta$  is the slope, and  $\epsilon$  is the error term. A linear model with ln-transformed dose as a continuous effect will be fitted. A point estimate and a 90% CI will be derived for the slope ( $\beta$ ), measure of the proportionality between the dose and the PK parameter. Evidence of dose proportionality for each PK parameter evaluated will be assessed by the 90% CI of each slope.

Appropriate dose-normalized PK parameters will also be assessed graphically for dose proportionality.

An ANOVA will be conducted on ln-transformed PK parameters, including  $AUC_{last}$ ,  $AUC_{inf}$ , and  $C_{max}$  to evaluate the effect of food on fenretinide in the recalled cohort (Cohort 4 vs Cohort 3). The study will calculate the differences between adjusted means and the standard error associated with these differences. The ratio of means will be calculated using the LSM for ln-transformed  $AUC_{last}$ ,  $AUC_{inf}$ , and  $C_{max}$  values. The 90% confidence interval (CI) for the difference between the fed and fasted conditions will be calculated for  $AUC_{last}$ ,  $AUC_{inf}$ , and  $C_{max}$  using ln-transformed concentration data. The CI will be expressed as a percentage relative to the LSM.

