**Table 5 Study Treatments – Tables and Figures**

Cohort: Actual Treatment	Treatment Label
Cohort 1: ISLA101 300 mg Fasted	ISLA101 300 mg Fasted
Cohort 2: ISLA101 600 mg Fasted	ISLA101 600 mg Fasted
Cohort 3: ISLA101 900 mg Fasted	ISLA101 900 mg Fasted
Cohort 4: ISLA101 TBD* mg Fed	ISLA101 TBD* mg Fed
Cohort x/4: ISLA101 TBD* mg	ISLA101 TBD* mg Fasted/Fed
Cohort 1-3: Placebo	Pooled Placebo
Cohort 4: Placebo (Fasted)	Placebo (Fasted)
Cohort 4: Placebo (Fed)	Placebo (Fed)
Cohort 1-3	All Subjects

\*One of the Cohort 1 to 3 Subjects (the highest tolerated dose-level cohort) will return for additional dose to determine the effect of food. Subjects participating in Cohort 4, the food effect cohort, will maintain the same treatment assignment from their fasted cohort.

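### The rule for who is recalled into the fed cohort is worded two ways, and Protocol 10.6 names Cohort 3 as comparator whichever cohort is recalled

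*Protocol*

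**What the plan says.** **Recall by tolerated dose.** The Synopsis states "The subjects in the highest tolerated dose-level cohort will also be administered ISLA101 under fed conditions, in a cross-over manner (Cohort 4" and, on the recall itself, "Following review of the safety data of the highest tolerated dose level, the subjects enrolled in this dose-level cohort will be recalled". The first paragraph of Protocol 3.1 says "The highest tolerated dose level cohort will then be evaluated in a fed condition (in a crossover manner", and Protocol 3.2 says "The highest tolerated dose will also be administered under fed conditions to assess any potential food effect (in a crossover manner". Protocol 3.3 and 5.1.1 agree. In the SAP, the footnote to Table 5 reads "One of the Cohort 1 to 3 Subjects (the highest tolerated dose-level cohort) will return for additional dose", and sections 6 and 6.9.2 use the same criterion.

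**Recall by dose received.** The third paragraph of Protocol 3.1 says "Safety data will be reviewed to identify the cohort that received the highest dose level under fasted condition". The next sentence acts on it: "The subjects in this cohort will be recalled to evaluate the PK of ISLA101 under fed conditions (8 subjects; Cohort 4". SAP 2.3 carries both wordings, as Protocol 3.1 does.

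**Comparator.** Protocol 10.6 runs the ANOVA "to evaluate the effect of food on fenretinide in the recalled cohort (Cohort 4 vs Cohort 3". The Synopsis text on PK analyses speaks only of the recalled cohort and gives no number. Footnote 9 of the schedule (Table 1 in both documents) counts Cohort 4 study days from dosing in Cohort 3. SAP 6.9.2 and Appendix 2 fit food as a fixed effect and subject as a random effect. SAP 7.1 declares no change from the protocol.

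**The concern.** The recall rule decides who takes a second dose, and at what level, once tolerability has been in question. Two wordings that can name different cohorts should not both stand. The plan provides for the case in which they diverge: Protocol 3.1 and 5.2 allow a lower, repeated or intermediate dose after safety review.

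The named comparator is a separate weakness. A food effect is meant to be read within subjects at one dose. If the recalled cohort is not Cohort 3, the contrast written in 10.6 mixes a dose difference and a between-subject difference into the fed/fasted ratio. The footnote to the SAP shell for Table 14.2.4 concludes that there is a food effect when point estimates fall outside 80 to 125%, so a dose difference could be reported as one.

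**Working it through.** **Figures in the plan.** No power or effect size is stated for the food-effect comparison. The only sample-size figure is about 24 subjects, which reproduces as 3 cohorts × 8 = 24. Each cohort has 6 active and 2 placebo, so 6 active subjects contribute to the food-effect comparison.

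**Which subjects each wording selects, on the planned doses (300, 600, 900 mg/m²):**

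| Situation | Tolerated wording | Received wording | Contrast in 10.6 read literally |
|---|---|---|---|
| 900 given and tolerated | Cohort 3 | Cohort 3 | Same subjects, same dose |
| 900 given, not tolerated | Cohort 2 | Cohort 3 | Tolerated wording: 600 fed vs 900 fasted, different subjects. Received wording: same subjects, same dose |

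In the second row the two problems are alternatives. Under the received wording the population conflicts with the other sections, but the contrast is correctly paired. Under the tolerated wording the population agrees with the majority of the text, and only the literal contrast fails.

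**Size of the mismatch in the second row, tolerated wording.** Inputs: doses from Protocol 3.1 and the power model from Protocol 10.6. With no food effect,

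expected ratio = (fed dose / fasted dose)^β = (600/900)^β.

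The documents give no value for β, so the slopes below are assumptions:

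| β | Expected ratio |
|---|---|
| 0.5 | 81.6% |
| 0.75 | 73.8% |
| 1 (dose-proportional) | 66.7% |
| 1.25 | 60.2% |
| 1.5 | 54.4% |

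The ratio falls below 80% once β exceeds ln(0.8)/ln(2/3) = 0.55. If the reference is the recalled subjects' own fasted period, the dose ratio is 1 and the expected ratio is 100% at any β.

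**Cohort number need not follow dose.** If 600 mg/m² were not tolerated and Cohort 3 were then given a lower dose, as Protocol 3.1 allows, the received wording would recall Cohort 2 and 10.6 would compare it with Cohort 3. For a Cohort 3 dose between 300 and 600 mg/m², the no-effect ratio under dose proportionality runs from 600/300 = 200% to 600/600 = 100%. This is another reason not to write a cohort number into the contrast.

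**What the SAP would do.** Section 6 presents Cohort 4 beside the fasted results of the highest tolerated cohort among Cohorts 1 to 3. Table 5 leaves that dose to be determined. Section 6.9.2 and the Appendix 2 code model the two periods within subject. None of these fixes Cohort 3.

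**The case against.** The best defence is that the disputed sentence is elliptical. It opens with a review of safety data, and no safety review is needed to find who received the largest dose. The same section has already named the highest tolerated cohort, and so do nearly all other passages. Several safeguards also stand between that sentence and a second dose:

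- The Safety Review Committee decides on continued safety and continued dosing (Protocol 3.6.1).
- The halting rules stop dosing in a cohort with dose-limiting events (5.3).
- The investigator confirms eligibility before each dose (8.1.2).
- Consent and eligibility are repeated at Day 9 (Table 1).

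On the contrast, Protocol 10.1 calls its analysis text an outline and defers to the SAP, which specifies the paired comparison. The objective is exploratory.

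Most of this stands, and it rules out several stronger readings:

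- *That a cohort which did not tolerate its dose would be dosed again.* This is a possible literal reading, not an expected outcome.
- *That population and contrast are both wrong if 900 mg/m² is not tolerated.* The table above shows that they are alternatives.
- *That the reported result would carry the 67% artefact and lose its pairing.* This follows only from 10.6 read literally, not from the SAP.
- *That the ratio could be 300/900 = 33% with Cohort 1 recalled.* Protocol 5.2 allows escalation past Cohort 2 only if it was judged well tolerated, so this would need a later reversal of that judgement.

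The defence does not supply the missing condition. The tolerability requirement in 5.2 attaches to moving to a higher dose, and no escalation follows Cohort 3. The recall rule is therefore where that cohort's tolerability has to be applied, and the sentence in 3.1 that triggers the recall omits it.

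**Conclusion.** The point holds as two wording conflicts that matter only if the recalled cohort might not be Cohort 3. The recall rule has two versions that diverge when the highest dosed cohort is not tolerated. Because the rule governs re-dosing of healthy volunteers, the passages must be reconciled. Which rule is right is for the sponsor and the Safety Review Committee, and is not judged here.

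The Cohort 3 comparator in Protocol 10.6 and the Cohort 3 anchor in footnote 9 fail if another cohort is recalled. The 67% figure assumes that Cohort 2 is recalled at 600 mg/m², that Cohort 3 received 900 mg/m², that there is no true food effect, that PK is dose-proportional, and that 10.6 is applied as written; its range is 82% to 54% for assumed slopes of 0.5 to 1.5. Since the SAP specifies the within-subject contrast, the analysis as programmed would probably be correct. What remains on the statistical side is a protocol-SAP difference that SAP 7.1 does not declare. If Cohort 3 receives and tolerates 900 mg/m², nothing goes wrong.

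**What to change.** 1. State one recall rule in the third paragraph of Protocol 3.1 and in SAP 2.3, consistent with the Synopsis, Protocol 3.2, 3.3 and 5.1.1, and SAP Table 5, section 6 and 6.9.2. The sponsor and the Safety Review Committee decide which rule applies throughout.
2. In Protocol 10.6, replace the cohort numbers with the fed period versus the fasted period of the same recalled subjects, as SAP 6.9.2 already models.
3. In footnote 9 of Table 1 in both documents, refer to the recalled cohort instead of Cohort 3.
4. If 10.6 is left as it is, record the difference in SAP 7.1.

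The cost is wording in two protocol sections, one SAP section and a shared footnote, plus the ethics approval that Protocol 12.1 requires for an amendment. Subject numbers, visits, samples and the SAP model do not change.
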